**Table 4: Study Procedures**

Study Procedure	Enrollment	Baseline	Telephone Call Follow Up Visits (24 Hour, 5 days, 2 weeks, 6 weeks, 10 weeks)	4 week visit	8 week visit	12 week visit (Study Exit)	Early Study Exit	Unscheduled Visit
Informed consent	x							
Inclusion/exclusion	x	x						
Demographics		x						
Medical History		x						
Medications		x	X	x	X	x	X	x**
Physical Assessment		x		x	X	x		x**
NYHA class		x		x	X	x		
MN Living with Heart Failure Questionnaire		x		x	X	x		
EQ-5D-5L Questionnaire		x			X			
6 Minute Walk Test		x		x	X	x		
Echo		x		x	X	x		x**
Blood Draw		x		x	X	x		x**
Initial Device Interrogation/Save-to-media		x		x	X	x	x	x**
Device Programming		x		x*	x*		x**	x**
Final Device Interrogation/Save-to-Media		x		x	X	x	x	x**
At least 30 minute observation period post device programming		x						
Symptom Assessment			X	x	X	x		x**

Study Procedure	Enrollment	Baseline	Telephone Call Follow Up Visits (24 Hour, 5 days, 2 weeks, 6 weeks, 10 weeks)	4 week visit	8 week visit	12 week visit (Study Exit)	Early Study Exit	Unscheduled Visit
Heart Rate (using finger oximeter)			X					
Crossover			As they occur					
System modifications	As they occur							
Adverse events (AEs)/Death	As they occur							
Device Deficiencies	As they occur							
Study deviations	As they occur							
Study Exits	As they occur							

\* See programming recommendations for the follow up visit

\*\* If deemed necessary by the investigator

Table 5 below specifies permitted time windows for the required subject visits. Should a subject miss a visit or the visit falls outside the pre-specified window, a study deviation must be reported and the original follow-up schedule maintained for subsequent visits. Data analyses will include follow-up visits, regardless of whether the visit occurs within the window. Therefore, a late visit is preferred over a missed visit but must be accompanied by a deviation.

**Table 5: Visit windows**

Visit	Must occur between	After reference visit
Baseline	0 - 30 days	Enrollment
24 Hour Phone Call	0-1 day	Baseline
5 Day Phone Call	2 - 8 days	Baseline
2 Week Phone Call	11 – 17 days	Baseline
Randomization – 4 week visit	21 – 35 days	Baseline
6 Week Phone Call	39 – 45 days	Baseline
8 Week Visit	49 – 63 days	Baseline
10 Week Phone Call	67 – 73 days	Baseline
12 Week Visit (Exit)	77 - 91 days	Baseline

## 10.6. Prior and Concomitant Medications

There are no medication restrictions in the study unless they are investigational and may confound the study results, in which case, prior approval would be needed from Medtronic.

At baseline, 4, 8, and 12 week follow up visits, all telephone call follow up visits, unscheduled visits, and early exit visits, cardiovascular medications and the use of insulin will be collected. Cardiovascular medications include: ACE inhibitors, ARBs, MRAs, antiarrhythmics, anti-coagulants and antiplatelets, antihypertensives, antilipidemics (incl. statins),  $\beta$ -blockers, calcium channel blockers, diuretics, digitalis, inotropes, nitrates, digoxin, and vasodilators.

## 10.7. Subject Consent

Informed consent is defined as a legally effective documented confirmation of a subject's voluntary agreement to participate in a particular clinical study after information has been given to the subject on all aspects of the clinical study that are relevant to the subject's decision to participate. This process includes obtaining an Informed Consent Form and an Authorization to Use and Disclose Personal Health Information/Research Authorization/other privacy language (data protection authorization) as required by law that has been approved by the study site's IRB, and Medtronic, and signed and dated by the subject and the Principal Investigator or an authorized designee. A subject may only consent after information has been given to the subject on all aspects of the clinical study that are relevant to the subject's decision to participate.

Prior to enrolling subjects, each site must have documented IRB approval of the Informed Consent Form (IC Form) and an Authorization to Use and Disclose Personal Health Information/Research Authorization/other privacy language (data protection authorization) as required by law. Any changes to a previously approved Informed Consent Form throughout the course of the study must be reviewed and approved by Medtronic and the IRB reviewing the application before being used to obtain consent or re-consent a study subject. The document(s) must be controlled (i.e. versioned and dated) to ensure it is clear which version(s) were approved by Medtronic and the IRB. All important new information should be provided in written form to new and existing subjects throughout the study. If relevant, all affected subjects must be asked to confirm their continuing informed consent in writing.

Prior to initiation of any study-specific procedures, informed consent must be obtained from the subject. Likewise, privacy or health information protection regulation may require subjects to sign additional forms to authorize sites to submit subject information to the study sponsor. Obtaining informed consent must be conducted by the principal investigator or an authorized designee, and the Informed Consent Form and an Authorization to Use and Disclose Personal Health Information/Research Authorization/other privacy language (data protection authorization), as required by law, must be given to the subject in a language he/she is able to read and understand.

The process of obtaining informed consent shall:

- Ensure that the principal investigator or an authorized designee obtains the informed consent process.
- Include all aspects of the clinical study that are relevant to the subject's decision to participate throughout the clinical study.
- Avoid any coercion or undue improper influence on, or inducement of the subject to participate.
- Not waive or appear to waive the subject's legal rights.
- Ensure the Informed Consent Form and an Authorization to Use and Disclose Personal Health Information/Research Authorization/other privacy language, (data protection authorization) as required by law, are given to the subject in a non-technical language the subject is able to read and understand.
- Provide ample time and opportunity for the subject to read and understand the Informed Consent Form to inquire about details of the study, and to consider participation. All questions about the study should be answered to the satisfaction of the subject.
- Include a personally dated signature of the subject acknowledging that their participation in the study is voluntary.
- Include a personally dated signature by the principal investigator or authorized designee responsible for obtaining the informed consent, as required by local law.
- Provide the subject with a copy of the Informed Consent Form and an Authorization to Use and Disclose Personal Health Information/Research Authorization/other privacy language (data protection authorization) as required by law.
- Ensure subjects are notified of any significant new findings about the study that become available during the course of the study which are pertinent to the safety and well-being of the subject, as this could impact a subject's willingness to participate in the study.

If the informed consent is obtained the same day the subject begins participating in study-related procedures, it must be documented that consent was obtained prior to participation in any study-related procedures. It is best practice for the process of obtaining the informed consent to be documented in the subject's case history, regardless of circumstance.

In the event the subject cannot read and/or write, witnessed (impartial third party) informed consent will be allowed, provided detailed documentation of the process of obtaining the informed consent is recorded in the subject's case history and the witness signs and dates the Informed Consent Form. Informed consent shall be obtained through a supervised oral process. An independent witness must be present throughout the process. The IC Form and any other information must be read aloud and explained to the prospective subject, if allowed by local law. The witness signs and personally dates the Informed Consent Form attesting that the information was accurately explained and that informed consent was freely given. The subject should "make his mark" (sign or otherwise physically mark the document so as to indicate consent) on the Informed Consent Form as well. The Informed Consent Form

should document the method used for communication with the prospective subject and the specific means by which the prospective subject communicated agreement to participate in the study.

The original of the signed Informed Consent Form must be filed in the hospital/clinical chart and/or with the subject's study documents.

The Informed Consent Form and an Authorization to Use and Disclose Personal Health Information/Research Authorization/other privacy language (data protection authorization) as required by law, must be available for monitoring, auditing and regulatory inspections. Any Medtronic personnel who support the initial programming of the elevated night pacing must be able to review the subject's signed and dated Informed Consent Form and verify its completeness prior to proceeding with the programming. In the event the designated Medtronic personnel identify the IC Form as being incomplete, the programming will not be allowed to occur until the consent of the subject can be adequately and appropriately obtained.

## **10.8. Enrollment**

A subject is considered enrolled when the Informed Consent Form has been signed and dated. The date the subject signed the Informed Consent Form and an Authorization to Use and Disclose Personal Health Information/Research Authorization/other privacy language (data protection authorization) as required by law, must be documented in the subject's medical records. Enrollment can be a stand-alone visit or can occur on the same day as the Baseline Visit. Once consent is obtained, report adverse events/deaths, study deviations and subject exits as they occur.

## **10.9. Baseline Visit**

The Baseline Visit must occur within 30 days after subject enrollment. The Baseline visit can be a stand-alone visit or can be performed on the same day as consent is obtained and documented in the subject's medical chart. If eligibility verification at the Baseline visit shows that the subject does not meet all inclusion and exclusion criteria the subject must be exited. The device programming should occur after all other study procedures are complete, except for the final device interrogation and save-to-media.

The subject will be provided at the Baseline Visit with a finger pulse oximeter monitor to use at home during the telephone follow-up visits to measure their heart rate. The finger pulse oximeter should be returned to the site at the study exit visit.

In the event a subject experiences symptoms at home after the Baseline visit, the subject will be instructed to seek medical help to determine the cause of the symptoms.

The following information is required to be collected at the Baseline visit:

- Verification of Inclusion/Exclusion criteria
- Subject Demographics
- Medical History
- Medications
- Physical Assessment (including height, weight, heart rate and blood pressure)
- NYHA Class
- MN Living with Heart Failure Questionnaire
- EQ-5D-5L Questionnaire
- 6 Minute Walk Test
- Echo\*
- Blood Draw\*\*

- Device Interrogation (initial)
- Save-to-Media (initial)
- Device Programming, see Table 6.
- Subject observation of at least 30 minutes to ensure the subject can tolerate 100 bpm pacing post programming
- Device Interrogation (final) - this needs to be completed at the end of the visit after programming has been completed
- Save-to-Media (final)

\*The Baseline echo must be sent to the Echocardiography Core Laboratory (echo core lab) for analysis, with a copy of the echo remaining at the site. Details of the echo core lab, type of echo to be performed, and the review process will be provided in an Echocardiography Handbook (provided under separate cover).

\*\* The baseline blood sample must be sent to the Blood Core Laboratory for analysis. Details of the blood core lab and the blood draw process will be provided under separate cover.

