### 7.2. Rationale

It is expected that up to 50 subjects may be enrolled to ensure approximately 30 subjects will have elevated night pacing programmed ON for the first 4 weeks in order to evaluate whether the therapy is symptomatic. Limitations to the programming of the Sleep Function requires subjects to have a lower

rate of 100bpm programmed between the time they leave the Baseline visit and 5am the next morning when "Bed Time" will set the Sleep Rate at the pre-study lower rate of 60-70bpm. At the 4 week visit, there will be a safety assessment. Measurements of NT-proBNP will be used to assess whether dilation of the heart is signalling worsening heart failure. A Troponin assay will be used to ensure the elevated night pacing therapy isn't leading to ischemia. Subjects will be randomized at 4 weeks to elevated night pacing ON or OFF in order to gather data on the dose-response of the elevated night pacing therapy. Some patients may have sensation of an elevated heart rate from this programming, making blinded randomization difficult to achieve. All subjects will be followed for at least 4 weeks following termination of the elevated night pacing therapy in order to evaluate whether changes in quality of life, 6 minute walk tests and echo measurements persist after the therapy is discontinued. Previous work in animal studies have shown that cessation of elevated pacing rates can reverse the dilation of the LV chamber; this study will monitor the time course of that reversal by serial echo measurements, 6 minute walk tests and activity counts, and quality of life assessments.

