**Figure 2: Sleep Function On During the Day**

The Sleep Function will be programmed to deliver the Sleep Rate between 5a.m. and 11:30pm, using a Bed Time of 5a.m. and a Wake Time of 11:30pm.

The Sleep Function was designed to operate in conjunction with Rate Responsive pacing; however, the Rate Profile Optimization feature that automatically optimizes was not developed with 5 hours of 100bpm imposed on patients. Therefore, Rate Profile Optimization will be turned OFF while the Sleep Function is programmed ON.

The Sleep Function is suspended following any parameter programming operations. If the Sleep Function is suspended, the pacing rate will immediately return to the programmed Lower Rate (100bpm per this protocol) until the next Bed Time is reached. At the initial programming visit of this protocol, subjects will be evaluated for whether they are symptomatic at a Lower Rate of 100bpm. Subjects will leave the Baseline visit experiencing a Lower pacing rate of 100 bpm until 5am the next morning, when Bed Time for the Sleep Function is reached. After the elevated pacing has been turned ON, any telemetry activation, such as programming, magnet application or CareLink transmission will suspend the Sleep Function and the pacemaker will immediately return to the Lower Rate of 100 bpm until 5am.

If a pacemaker reaches Estimated Replacement Indicator (ERI), the device will automatically turn OFF the Sleep Function and reprogram the pacemaker to VVI 65 mode.

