## 9.3. Inclusion Criteria

Subjects must meet all of the following inclusion criteria to be eligible to participate in the study:

INC 1: Subject has had a market released dual chamber Medtronic Pacemaker with a Sleep function for at least 3 months

INC 2: Subject is stable on current medications

INC 3: Subject has dyspnea with exertion or diagnosed as NYHA Class II or III heart failure.

INC 4: Subject has had a prior Echo in past 6 months with: EF  $\geq$  50% and Diastolic volume  $\leq$ 80 ml/m^2

INC 5: Subject has evidence of hypertrophy (indexed to body surface area: men 115 g/m^2, women 95 g/m^2 or indexed to height: men 49.2 g/m2.7, women 46.7 g/m2.7) or Relative Wall thickness  $>$ 0.42, or Wall Thickness  $\geq$ 1.2cm (posterior wall)

INC 6: Subject is willing to sign and date the study Informed Consent Form (IC Form) and Authorization to Use and Disclose Personal Health Information/Research Authorization/other privacy language (data protection authorization) as required by law

INC 7: Subject is 18 years of age or older, or of legal age to give informed consent per local law

INC 8: Subject is expected to remain available for follow-up visits

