### 10.11. Randomization (4 Week Follow-Up)

Subjects will be assigned to a group at random during the randomization visit. Randomization will occur at 4 weeks.

Subjects will be randomized in a 2:1 ratio to the Elevated Night Pacing ON or to the Elevated Night Pacing OFF group.

Sites will receive this randomization assignment from the randomization schedule, which is automatically populated on the eCRF.

Procedures to be performed and data to be collected at Randomization include:

- Physical Assessment (including weight, heart rate, symptoms, and blood pressure)
- Medications
- NYHA Class
- MN Living with Heart Failure Questionnaire
- 6 Minute Walk Test
- Echo\*
- Blood Draw\*\*
- Randomization assignment
- Device Interrogation/ (initial)
- Save-to-Media (initial)
- Device Programming, see Table 7: Programming Recommendations at 4 Week Follow-Up
- Device Interrogation (final) - this needs to be completed at the end of the visit after programming has been completed
- Save-to-Media (final)
- Adverse Events (report new/assess ongoing AEs), Study Deviations, System Modifications, Device Deficiencies, Crossovers (as they occur)

\*The echo must be sent to the Echo Core Laboratory for analysis, with a copy of the echo remaining at the site. Details of the Echo Core Laboratory, type of echo to be performed, and the review process will be provided in an Echocardiography Handbook (provided under separate cover).

\*\* The blood sample must be sent to the Blood Core Laboratory for analysis. Details of the blood core lab and the blood draw process will be provided under separate cover.

For any subject who has an abnormal NT-proBNP, troponin or LVEF measurement as defined in the Safety Assessment (Section 10.19. Assessment of Safety) and the investigator elects to discontinue elevated night pacing, a subsequent visit will be necessary for the elevated night pacing to be programmed OFF if the subject was randomized to the elevated pacing ON arm. The subject should continue to be followed through the 12 week visit.

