### **12.1. Adverse Events**

Adverse Event definitions are provided in Table 10. To ensure that all AEs that are potentially relevant are collected, the following will be collected throughout the study duration, starting at the time of signing the Informed Consent Form:

- All system related AEs
- All programming related AEs
- All cardiovascular related AEs
- All Serious Adverse Events (SAEs), regardless of relatedness

In order to fully understand intolerable symptoms and mitigate any safety concerns about elevated night pacing, for any subject that exits the study because of intolerable symptoms, the enrolling site should report any associated programming related AEs. Reporting of these events to Medtronic will occur on an Adverse Event (AE) eCRF. Documented pre-existing conditions are not considered AEs unless the nature or severity of the condition has worsened.

For AEs that require immediate reporting (see Table 12), initial reporting may be done by phone, fax, or on the eCRF completing as much information as possible. The original completed AE eCRF must be submitted to Medtronic as soon as possible.

Each adverse event must be reported separately. Any medication, whether cardiovascular or not, associated with the treatment of an adverse event must be reported.

Subject deaths are also required to be reported. Refer to Section 12.6. Subject Death for Subject Death collection and reporting requirements.

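### No symptom questions are scheduled before pacing starts, so early symptom reports in the single-arm phase have no like-for-like baseline

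*Protocol*

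**What the plan says.** **Purpose of the first 4 weeks.** Protocol 7.2 wants about 30 subjects to have "elevated night pacing programmed ON for the first 4 weeks in order to evaluate whether the therapy is symptomatic". Section 14 describes this phase as single-arm and unblinded.

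**Who enters.** INC 3 in section 9.3 reads "Subject has dyspnea with exertion or diagnosed as NYHA Class II or III heart failure". Table 9 lists dizziness, palpitations, heart racing, shortness of breath and difficulty sleeping as possible harms of sustained elevated pacing.

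**When symptoms are asked.** In Protocol Table 4 and SAP Table 1 the Symptom Assessment row is blank at Enrollment and Baseline. It is marked at all five calls and at weeks 4, 8 and 12. Section 10.9 specifies for Baseline "Physical Assessment (including height, weight, heart rate and blood pressure", while section 10.11 specifies for week 4 "Physical Assessment (including weight, heart rate, symptoms, and blood pressure". Sections 10.12 and 10.14 also name symptoms. Section 10.10 introduces a standard question set for the calls, all of which follow the start of pacing.

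**The adverse event rule.** Section 12.1 says "Documented pre-existing conditions are not considered AEs unless the nature or severity of the condition has worsened".

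**Timing of the first call.** The Synopsis and section 10.10 place it at 24 hours after Baseline. In Table 5 the row "24 Hour Phone Call" has a window of day 0 to day 1. The text with Figure 2 in section 8.4 says "Subjects will leave the Baseline visit experiencing a Lower pacing rate of 100 bpm until 5am the next morning".

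**The concern.** Before randomization there is no concurrent control. Each subject's own state before pacing is the only reference for judging whether a symptom on therapy is new or worse. In a population enrolled for dyspnea or NYHA II/III, some subjects may report shortness of breath or poor sleep on any given day whether or not they are paced. If the questions are first asked after pacing is ON, those reports could be read as effects of pacing or set aside as long-standing, and nothing collected with the same questions would settle which. The gap matters most for the first three calls, which are the closest look at first exposure. A pre-therapy answer cannot be obtained prospectively once pacing has begun.

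**Working it through.** The plan states no figure to reproduce on this point, so the check sets the schedules side by side and adds a small illustration.

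**1. What is available before pacing and at each contact up to week 4** (Protocol Table 4; SAP Table 1 agrees)

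| Contact | Symptom Assessment | NYHA class | MNLWHF |
|---|---|---|---|
| Baseline, before programming | no | yes | yes |
| 24 hour, 5 day and 2 week calls | yes | no | no |
| Week 4 visit | yes | yes | yes |

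No instrument is collected both before pacing and at the calls. At week 4, NYHA and MNLWHF allow a before-and-after comparison. However, SAP 7.9.4 analyses the MNLWHF as the sum of its 21 items, so its sleep question (mentioned in Protocol section 7) is not examined separately.

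**2. Why prevalence on therapy alone is not enough.** Let b be the proportion with a symptom before pacing and t the proportion of the remainder who develop it. Ignoring resolution, prevalence on therapy is b + (1 − b)t. The documents give neither b nor t, so these values are assumptions. With 30 subjects:

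- b = 0.40, t = 0: 0.40, or 12 subjects, none of them new.
- b = 0.20, t = 0.25: 0.20 + 0.80 × 0.25 = 0.40, or 12 subjects, of whom 6 are new.

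The observed count is 12 in both cases. With t = 0 and b = 0.30, 0.50 or 0.70, the count on therapy would be 30 × b = 9, 15 or 21 with no effect of pacing at all.

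**3. What the later randomized contrast can add.** If all 30 are randomized 2:1, there are 20 ON and 10 OFF. The 95% half-width for a difference in symptom proportion, at a common proportion p, is 1.96 × √[p(1 − p)(1/20 + 1/10)]:

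- p = 0.1: 0.23
- p = 0.3: 0.35
- p = 0.5: 0.38

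Power for a 30-point difference (two-sided 0.05, assumed OFF rates 0.1 to 0.5) is 0.33 to 0.40. The contrast is weak but not absent. It includes only subjects who completed 4 weeks of pacing, so it does not address symptoms at first exposure.

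**4. The first call.** Counting nights from programming, a day-0 call is preceded by 0 paced nights and a day-1 call by 1. If the call is made on day 0, the next one (5 Day window, days 2 to 8) comes after 2 to 8 nights.

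**The case against.** The strongest case on the other side has five parts.

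- **The 4-week endpoint does not need a symptom baseline.** Protocol 14.1.1 and SAP 7.9.1 count subjects who remain in the study, and the SAP treats any earlier exit as related to symptoms or safety. This stands. It also means that the endpoint does not describe symptoms in those who stay, and the SAP has no analysis of the symptom-assessment data.
- **Baseline symptom status is partly recorded.** NYHA class, MNLWHF, EQ-5D-5L, medical history and verification of INC 3 all come before programming. SAP 7.6 allows symptoms from medical history to be summarised. This stands for dyspnea and, in part, for sleep. It is weakest for palpitations and dizziness, and it gives no matching measurement at the calls.
- **The forms are not in the documents.** The eCRFs and the standard questions are provided separately. Baseline history fields might match the call questions, or the calls might ask about new or worsened symptoms. Neither can be confirmed or excluded. The point therefore rests on what the protocol and SAP schedule.
- **Symptoms are evaluated at the programming visit.** Section 8.4 says subjects are assessed for symptoms at 100 bpm, and section 10.9 requires at least 30 minutes of observation. Both follow programming, so they check acute tolerance and are not a pre-pacing reference.
- **The wording contrast between visits is thin.** The Synopsis omits symptoms from Physical Assessment at weeks 4, 8 and 12 as well, and the lists are not exhaustive. The evidence that carries the point is the blank cells in Table 4 and SAP Table 1.

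On the first call, pacing at 100 bpm begins at the visit, so a same-day evening call does capture some waking exposure. Later contacts cover paced nights.

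**Conclusion.** The point holds in a limited form. No scheduled assessment with the standard symptom questions precedes pacing in any of the roughly 30 subjects. In a phase intended "in order to evaluate whether the therapy is symptomatic", reports at the 24 hour, 5 day and 2 week calls cannot be reliably separated from pre-existing symptoms. No sample size, endpoint or planned test changes. The counts in the illustration depend on assumed prevalences and show the mechanism, not an expected result.

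Three stronger readings might be inferred, and the documents do not support them:

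- **That the trial cannot tell whether the therapy is symptomatic.** Exits, NYHA, MNLWHF, the post-programming evaluation, the ON/OFF period and the OFF period after week 8 all give partial information.
- **That the worsening rule for adverse events cannot be applied.** The rule concerns documented conditions, and medical history is required at Baseline. A like-for-like symptom record would support the judgement, but its absence does not make the rule unworkable.
- **That the first call is uninformative.** The mismatch is between a 24-hour label and a window that admits a same-day call, before the first full paced night and the 5am changeover. It is a secondary inconsistency.

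**What to change.** 1. Mark Symptom Assessment at Baseline in Protocol section 10.9, Protocol Table 4 and SAP Table 1. State that the same standard questions used at the calls are asked before device programming. Section 10.9 already places programming after the other procedures, so the order of the visit does not change.
2. Add to the SAP a descriptive summary, by symptom, of reports at 24 hours, 5 days, 2 weeks and 4 weeks, classified as absent, unchanged, new or worsened against the Baseline answer. No test is needed. Subjects without a Baseline answer should be counted and shown separately.
3. Reconcile the 24-hour timing in the Synopsis and section 10.10 with the window in Table 5 and the pacing timeline in sections 8.4 and 10.9.1. The choice of call timing is for the sponsor and investigators.

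The cost is a few minutes per subject at an existing visit with an existing question set, a Baseline entry on the case report form if there is none, and short edits to the protocol and SAP. The sample size is unaffected.
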